11.4. Pregnancy

Parent(s)/guardian of female patients who are of childbearing potential must be instructed to notify the investigator immediately if their child becomes pregnant or if they suspect she is pregnant during the trial. All initial reports of pregnancy in female patients must be reported by trial site personnel using the appropriate pregnancy form in EDC within 24 hours of their knowledge of the event. Abnormal pregnancy outcomes (e.g., spontaneous abortion, fetal death, stillbirth, congenital anomalies, or ectopic pregnancy) are considered SAEs and must be reported using the SAE form. If a patient becomes pregnant during the trial, treatment must be discontinued.

The investigator must follow the pregnancy until its outcome is known and the newborn infant is 1 month of age. The investigator must report information about the pregnancy, pregnancy outcome, and health of the newborn infant(s), as well as AEs in connection with the pregnancy, and AEs in the fetus and newborn infant.

11.5. Precautions

Normal precautions taken for a clinical trial, including the provision of emergency equipment, will be taken during this trial. Qualified and well-trained physicians and medical staff will instruct patients' parents. During a patient's participation in the trial, the investigator should ensure that adequate medical care is provided to patients for any AEs, including clinically significant laboratory values related to the trial. The investigator should inform the patient's parents when medical care is needed for intercurrent illnesses of which the investigator becomes aware.

For further information on safety precautions for dasiglucagon, refer to the current version of the IB.

11.6. Safety Committee

An internal Zealand Safety Committee is constituted to perform ongoing safety surveillance of clinical trials with dasiglucagon, including this trial.

If safety signals or concerns are observed, whether based on reported SAEs, review of all AEs and laboratory parameters reported, or any other notification of significant findings, the Safety Committee will respond appropriately to protect the safety of the patients. The Safety Committee meets quarterly and additionally on an ad hoc basis as needed.

11.7. Independent Data Monitoring Committee

An independent data monitoring committee (DMC) will be established for this trial and follow the procedures outlined in the DMC Charter.

12. STATISTICS

12.1. Statistical Hypotheses

This section details the null hypotheses for this trial, which are presented in the form H_{ij} , where i = treatment period (i = 1) and j = hypothesis number (j = 1, 2, 3, 4).

The hypothesis relating to the primary endpoint is:

H₁₁: Hypoglycemia event rate dasiglucagon = hypoglycemia event rate soc only

The hypotheses relating to the key secondary endpoints are:

H₁₂: Increase in fasting tolerance dasiglucagon = increase in fasting tolerance soc only

H₁₃: CGM percent time in range dasiglucagon = CGM percent time in range SOC only

H₁₄: Clinically significant hypoglycemia event rate _{dasiglucagon} = clinically significant hypoglycemia event rate _{SOC only}

A fixed-sequence statistical strategy will test the primary (Section 6.2.1) and 3 key secondary endpoints of Treatment Period 1 (Section 6.2.2) in a pre-defined order, all at the same significance level ($\alpha = 0.05$ to maintain an overall Type I error rate of at maximum $\alpha = 0.05$; see statistical analysis plan [SAP] for more details), moving to a second endpoint only after a success on the previous endpoint.

The test hierarchy is:

Treatment Period 1

H₁₁: Hypoglycemia event rate (measured by SMPG) during Weeks 2-4 of the treatment period (primary endpoint)

H₁₂: Increase in fasting tolerance (i.e., time from meal to PG <70 mg/dL) from baseline to Weeks 2-4 of the treatment period (key secondary endpoint)

H₁₃: CGM percent time in range 70-180 mg/dL (3.9-10.0 mmol/L) during Weeks 2-4 of the treatment period (key secondary endpoint)

H₁₄: Clinically significant hypoglycemia event rates, defined as average weekly number of events <54 mg/dL (3.0 mmol/L) (as detected by SMPG) during Weeks 2-4 of the treatment period (key secondary endpoint)

12.2. Sample Size Determination

Patients will be randomized into the trial if they have at least 3 events of hypoglycemia on average per week, as recorded in the diary during the 2 weeks prior to randomization. It is assumed that patients continuing on standard of care will maintain a similar level through Treatment Period 1, with the number of hypoglycemia events (PG <70 mg/dL or 3.9 mmol/L) during Weeks 2-4, as detected by SMPG following a Poisson distribution with a mean of 9. The trial is powered to detect a treatment effect of 50%, hence, assuming that the number of hypoglycemia events reported for patients in the dasiglucagon group during Weeks 2-4 will follow a Poisson distribution with a mean of 4.5. At the final analysis, 32 patients will have 99% power testing at a 0.05 significance level. The overall alpha level is strongly controlled in this setting, remaining at or below 0.05.

12.3. Analysis Populations

Three analysis populations are defined for this trial:

- The Safety Set: defined as all patients administered any randomized treatment. This population will be used to provide descriptive summaries of safety data. Patients will be summarized by treatment period according to treatment received
- The Full Analysis Set (FAS): defined as all patients in the Safety Set who have a valid baseline efficacy assessment. This population will be used to analyze efficacy data. Patients will be analyzed by treatment period according to planned treatment
- The Per Protocol (PP) Analysis Set: defined as all patients in the FAS without any major protocol deviations. This population will be used to analyze primary and key secondary endpoints as a supportive analysis. Patients will be analyzed according to planned treatment for the first treatment period only

Inclusion in the analysis populations will be determined prior to database lock.

12.4. Statistical Analyses

This section presents a summary of the planned statistical analyses. A SAP that describes the details of the analyses to be conducted will be finalized prior to database lock.

Unless otherwise indicated, all testing of statistical significance will be 2-sided with a significance level of $\alpha = 0.05$ to maintain an overall Type I error rate of $\alpha = 0.05$; see SAP for more details.

For analyses involving trial site, if the number of patients per site is small, sites may be pooled for analysis, or omitted from statistical models. The final determination will be made prior to database lock.

Continuous endpoints will be summarized with number (n), mean, SD, median, minimum, and maximum. In addition, change from baseline values will be calculated at each time point and summarized descriptively. For categorical endpoints, descriptive summaries will include counts and percentages.

Immunogenicity data will be analyzed descriptively. No statistical tests are planned. Baseline ADA-positive patients will be calculated as a percentage of the total number of patients whose baseline samples were tested for ADA. Overall ADA incidence, the combined results of treatment induced, and treatment boosted ADA-positive patients, will be calculated as a percentage of the total number of evaluable patients, excluding baseline positive patients without any samples available after drug administration. Titers will be reported as median and interquartile range.

Graphical presentations of selected endpoints will be prepared and will be outlined in the SAP.

12.4.1. Trial Patients and Demographics

12.4.1.1. Disposition and Withdrawals

The numbers of patients randomized, completing, and withdrawing, along with reasons for withdrawal, will be tabulated overall and by treatment group. The number of patients in each analysis population will be reported.

12.4.1.2. Protocol Deviations

Protocol deviations will be provided in a listing and summarized if appropriate.

12.4.1.3. Demographics and Other Baseline Characteristics

Demographic and baseline characteristics (including age, sex, race, ethnicity, weight, and length/height) at screening will be summarized using descriptive statistics. No formal statistical analyses will be performed.

Prior and concomitant medications and procedures will be summarized by treatment group and the number and percentage of patients taking each medication, classified using World Health Organization Drug Dictionary Anatomical Therapeutic Chemical classes and preferred term (PT).

12.4.2. Duration of Exposure and Compliance

Trial drug administration will be summarized in terms of each patient's mean, mode, and final dose, and in terms of duration of exposure. Descriptive statistics for these quantities, including the mean, median, SD, minimum, maximum, and quartiles, will be provided by treatment group.

12.4.3. Efficacy Analyses

The efficacy analysis will be separated into 3 categories:

- 1. Treatment Period 1, FAS
- 2. Treatment Period 1, PP (primary and key secondary endpoints only)
- 3. Treatment Period 2, FAS

12.4.3.1. Primary Analysis

Primary Endpoint (Treatment Period 1)

The primary efficacy endpoint is the hypoglycemia event rate during Weeks 2-4 of Treatment Period 1. A hypoglycemia event is defined as PG <70 mg/dL or 3.9 mmol/L, as detected by SMPG. The analysis will be based on the hypoglycemia events reported in the eCRF. Baseline is defined as the average weekly number of hypoglycemic events during the 2-week baseline period. Weeks 2-4 of Treatment Period 1 is defined as the average weekly number of hypoglycemic events across the last 3 weeks of the treatment period. The hypothesis:

H₁₁: Hypoglycemia event rate $_{dasiglucagon}$ = hypoglycemia event rate $_{soc\ only}$ will be analyzed by using negative binomial regression, with treatment group as a fixed effect and baseline hypoglycemic rate as a covariate. The log-transformed number of days in Treatment Period 1 will be used as an offset variable. The null hypothesis is that there is no difference in the incidence of average weekly number of hypoglycemic events between the 2 treatment groups, which will be tested at the significance level of α =0.05.

The primary analysis will estimate the treatment effect based on the de facto (treatment policy) estimand. All available data in the form of actual measurements will therefore be included in the analysis, irrespective of adherence to treatment or use of subsequent therapy. Missing data will be imputed using multiple imputation (MI) methodology as described in Section 12.4.3.4.

As a sensitivity analysis, the primary endpoint will also be analyzed without imputation of missing data; however, this analysis will not be included in the fixed-sequence hierarchical testing strategy. Similarly, the primary endpoint may be analyzed excluding post-baseline data collected after trial drug discontinuation/completion.

12.4.3.2. Key Secondary Analyses

Treatment Period 1

The key secondary endpoint of clinically significant hypoglycemia (<54 mg/dL [3.0 mmol/L]) event rates will be analyzed using a negative binomial regression, with treatment group as a fixed effect and baseline hypoglycemic rate as a covariate. Percent time in range (i.e., the percent time between 70 mg/dL [3.9 mmol] and 180 mg/dL [10.0 mmol], inclusive, as measured by CGM, where percent time is calculated as [number of minutes in range/total number of minutes patient is wearing CGM] * 100%) will be analyzed by using an ANCOVA, with treatment group and region as fixed effects and baseline time in range as a covariate. Increase in fasting tolerance (i.e., change from baseline in time from meal to PG <70 mg/dL) will be analyzed similarly, using an ANCOVA, with treatment group and region as fixed effects and baseline fasting tolerance as a covariate. Baseline is defined as the mean weekly value during the 2-week baseline period; Weeks 2-4 of Treatment Period 1 is defined as the mean weekly value across the last 3 weeks of the treatment period.

Missing data will be imputed in a similar manner to the primary endpoint. Analyses will be repeated without imputation of missing data; as with the primary endpoint, these analyses will not be included in the fixed-sequence hierarchical testing strategy.

12.4.3.3. Secondary and Other Efficacy Analyses

For the remaining efficacy endpoints, continuous and categorical endpoints will be presented using summary statistics or frequencies, respectively; no inference will be performed. Missing data will not be imputed.

The secondary efficacy endpoints related to the use of gastric carbohydrates will be evaluated descriptively only in the subgroup of patients with gastrostomy or NG tube at baseline.

Resource Utilization

The number and percentage of patients with admissions/emergency department visits for glycemia, hospitalizations due to CHI, visits to health care providers (family doctor, specialists, etc.) caused by CHI or CHI-related events, and need for home visits by parameters will be summarized. Additionally, number and length (in days) of hospitalizations due to CHI, number of visits to health care providers (family doctor, specialists, etc.) caused by CHI or CHI-related events, and number of home visits by paramedics will be summarized.

Quality of Life

Quality of life will be assessed by the PedsQL and a CHI disease-specific questionnaire (Appendix B). For each item of the PedsQL instrument (parent), a 5-point response scale is used (0 = never, 1 = almost never, 2 = sometimes, 3 = often, 4 = almost always). Items are reverse-scored and linearly transformed to a 0-100 scale $(0 \to 100, 1 \to 75, 2 \to 50, 3 \to 25, 4 \to 0)$ so that higher scores indicate better health-related QoL (less negative impact). Scale scores are computed as the sum of the items divided by the number of items answered (this accounts for missing data). If more than 50% of the items in the scale are missing, the scale score is not computed. Change from baseline for PedsQL for each of the scales (physical functioning, emotional functioning, social functioning, and school functioning) and summary scores (total scale score, physical health summary score, and psychosocial health summary score) will be summarized.

Answers to each question on the CHI disease-specific questionnaire will be summarized using frequencies at each relevant visit.

12.4.3.4. Imputation of Missing Data

For analysis of primary and key secondary endpoints, a jump-to-control (J2C) MI method, with SAS procedures PROC MI and PROC MIANALYZE, will be performed, including demographics and baseline characteristics in a first MI analysis. Due to the expectation of rapid metabolism and excretion of trial drug, it is expected that efficacy would be similar to the control group in cases of premature treatment discontinuation; thus, the J2C method is appropriate to handle missing values in this situation (considered missing not at random [MNAR]). Any missing values occurring before the patient discontinues/completes treatment will be imputed based on the data from the same treatment group (considered missing at random [MAR]).

The analysis will have 3 broad components: i) the MI process for the SOC only data; ii) the MI process for the dasiglucagon + SOC patients' data; and iii) the analysis model that will be used to draw inference regarding the primary causal estimand, along with the method for combining the results across the multiply imputed datasets. The seed to be used in the analysis is 12255070. The algorithm will use 20 burn-in iterations before each imputation, and 1000 imputed datasets will be created for the analysis for each of steps i and ii.

To accommodate both monotone and non-monotone missingness patterns, imputed values will be generated by a pattern mixture imputation model under the MNAR assumption using the fully conditional specification (FCS) method. The primary analysis will be performed using a negative binomial regression model from which hypoglycemia incidence density ratios (IDR) and 95% confidence intervals are obtained, along with the model parameter estimates, standard errors, and *p* values; analyses of the key secondary endpoints will be performed using the appropriate modeling. The final step in the imputation will involve using PROC MIANALYZE to derive valid univariate inference for these parameters. Multivariate inference based on the Wald test will be derived to test for the significance of these parameters.

Complete details for conducting this analysis will be outlined in the SAP.

12.4.4. Safety and Tolerability Analyses

Safety analyses will be conducted using data from the Safety Population (as defined in Section 12.3). Safety assessments will include the evaluation of AEs; clinical laboratory assessments (hematology, biochemistry, and ADAs); vital signs, physical examinations; ECGs, echocardiography, and local tolerability issues. No formal inferential analyses will be conducted for safety variables, unless otherwise noted.

Baseline is defined as the last non-missing assessment before first dose in each treatment period. All safety analyses will be summarized by treatment received within treatment period and by trial visit, if applicable.

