9.2. Treatments Administered

In Treatment Period 1, patients will receive SOC only or SOC plus dasiglucagon for 4 weeks based on their treatment assignment. In Treatment Period 2, all patients will receive SOC plus dasiglucagon for 4 weeks.

Dosing of dasiglucagon will approximate continuous infusion by delivering small doses at frequent intervals via the infusion pump.

The pump administers $0.000025 \text{ mL/dose} \sim 0.1 \mu\text{g/dose}$ (4 mg/mL formulation):

- $10 \mu g/hour \sim 0.5 \mu g every 3 min$
- $20 \mu g/hour \sim 1 \mu g every 3 min$
- $30 \mu g/hour \sim 1.5 \mu g every 3 min$
- $40 \mu g/hour \sim 2 \mu g every 3 min$
- 50 μ g/hour ~ 2.5 μ g every 3 min
- $60 \mu g/hour \sim 3 \mu g every 3 min$
- $70 \mu g/hour \sim 3.5 \mu g every 3 min$

Plasma glucose assessments will be performed regularly (at least 3 times daily, preferably before main meals, and as instructed by the investigator) throughout the trial to guide adjustments to the gastric dextrose infusion and/or trial drug product upon the investigator's discretion.

Dasiglucagon treatment will be initiated at 10 μ g/hr (t=0). Every 2 hours (t=2, 4, 6, etc.), the dose will be increased by an additional 10 μ g/hr until either:

- 1. The patient is weaned off entirely from gastric dextrose infusion and/or glucose-fortified feeds, or
- 2. Plasma glucose during the last 2 hours was consistently above 120 mg/dL (6.7 mmol/L), or
- 3. The maximum trial drug product infusion rate of 70 μg/hr is reached, or
- 4. Adverse events emerge that are considered to be related to dasiglucagon (e.g., nausea and vomiting) and limit further dose escalation

The dose of dasiglucagon should not be escalated beyond reaching the treatment objectives of PG in the range of 70-120 mg/dL (3.9-6.7 mmol/L) while approaching a normal feeding regimen according to age.

The 2-hour dose-adjustment interval will allow plasma drug levels to approach approximately steady-state before the dose is further increased. The maximum dose of trial drug product that can be administered over the first 24 hours is shown in Table 1. The maximum cumulative dose over the first 24 hours is 1.26 mg.

After the first 24 hours, the dose of dasiglucagon can still be modified to optimize each patient's treatment and to reduce gastric dextrose infusions. The maximum dose of dasiglucagon will be 70 µg/hr, corresponding to a maximum of 1.68 mg per day.

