9.5. Method of Assigning Patients to Treatment Groups

In Treatment Period 1, patients will be randomly assigned in a 1:1 ratio to receive either SOC only or SOC plus dasiglucagon for 4 weeks using a block randomization scheme stratified by region US/non-US). In Treatment Period 2, all patients will receive SOC plus dasiglucagon for 4 weeks. The stratification by region addresses the difference in practice of treatment for CHI, especially the prominent difference in frequency of sub-total pancreatectomy for diffuse CHI between US/non-US.

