10.1. Trial Duration

The overall trial duration is expected to be 15 months.

The sequence and maximum duration of the trial periods will be as follows:

- 1. Screening: at least 14 days up to 28 days
- 2. Treatment Period 1: 4 weeks
- 3. Treatment Period 2: 4 weeks
- 4. Follow-up Period: 4 weeks

The maximum trial duration for each patient is approximately 16 weeks. The dasiglucagon treatment duration for each patient is 4 or 8 weeks.

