If subject discontinues trial before reaching Week 9:			
Week 2	Days 8 – 14	Date 1 date + 7 days	Earliest of Analysis Start Date + 6 days, or date of trial discontinuation
Week 3	Day 15 – 21	Date 1 date + 14 days	Earliest of Analysis Start Date + 6 days, or date of trial discontinuation
Week 4	Days 22 – 28	Date 1 date + 21 days	Earliest of Analysis Start Date + 6 days, or date of trial discontinuation
Weeks 2-4	Days 8 – 28	Same as Week 2 Analysis Start Date	Same as latest of Week 2, Week 3, or Week 4 Analysis Stop Date
Week 5	Days 29 – 35	Week 5 date	Earliest of Analysis Start Date + 6 days, or date of trial discontinuation
Week 6	Days 36 – 42	Week 5 date + 7 days	Earliest of Analysis Start Date + 6 days, or date of trial discontinuation

Study Week	Planned Days	Analysis Start Date	Analysis Stop Date
Week 7	Days 43 – 49	Week 5 date + 14 days	Earliest of Analysis Start Date + 6 days, or date of trial discontinuation
Week 8	Days 50 – 56	Week 5 date + 21 days	Earliest of Analysis Start Date + 6 days, or date of trial discontinuation
Weeks 6-8	Days 36 – 56	Same as Week 6 Analysis Start Date	Same as latest of Week 6, Week 7, or Week 8 Analysis Stop Date

- **Study Visit** = in-clinic visit as per the schedule of events, to be used for assessments that can only occur during a clinic visits (e.g., PedsQL, safety assessments like clinical laboratory assessments and vital signs).
- **Change from baseline** = value at current time point – value at baseline.
- **TEAE** = an AE with an onset at the time of or following the start of treatment with the trial drug (dasiglucagon + SOC arm) or date/time of randomization (SOC only arm) through the Follow-up visit or Early Termination visit, whichever occurs first.
- **PK Clearance:**

$$CL/f \text{ (L/h)} = R_0/C_{ss}$$

where R_0 = infusion rate (pmol/h) and C_{ss} = concentration at steady state (pmol/L), weight ($1\mu\text{g/kg/hr} = 295.7 \text{ nmol/kg/h}$)

- **SMPG-detected Hypoglycemia episode** = PG <70 mg/dL or 3.9 mmol/L, as detected by SMPG and reported in the eCRF. A single hypoglycemia episode is defined as up until 60 minutes from the start of the episode even if normoglycemia (>70 mg/dL) is not reached within this time. A new episode of hypoglycemia is to be reported when the next PG value below 70 mg/dL (3.9 mmol/L) is measured. Episodes are defined as the ones entered in the eCRF, no statistical programming will be done to define an episode.

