8.4.3. CHI Related Hospitalization

The frequencies and percentage of patients with admissions/emergency department visits for hypoglycemia, hospitalizations due to CHI or CHI-related events, visits to health care providers (family doctor, specialists, etc.) caused by CHI or CHI-related events, and need for home visits by paramedics due to hypoglycemia will be summarized by treatment group at each study week (as defined in Section 6.1.7) for each treatment period.

Additionally, number and length (in days) of hospitalizations due to CHI, number of visits to health care providers (family doctor, specialists, etc.) caused by CHI or CHI-related events, and number of home visits by paramedics due to hypoglycemia will be summarized descriptively by study week and treatment group for the patients in FAS based on treatment period.

9. Safety and Tolerability Analysis

Safety assessments will include the evaluation of AEs, clinical laboratory assessments (hematology, biochemistry, and ADAs), vital signs, physical examinations; electrocardiograms (ECGs), echocardiography, and local tolerability issues. No formal inferential analyses will be conducted for safety variables, unless otherwise specified. All safety analyses will be summarized by treatment received within treatment period and also by active treatment (Dasiglucagon pooling data of treatment period 1 and 2) and by study visit, if applicable.

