9.4. Electrocardiograms

An ECG will be performed at Screening and Weeks 2, 5, 6, 9, and 12. Moreover, for patients enrolled under version 9 of protocol and later, ECG is also measured at the start of the visit and at 24 ± 4 hours after initiation of trial drug for patients initiating treatment. Those data will be included in descriptive analysis.

Descriptive summaries of observed and change from baseline values will be presented for continuous ECG measures of heart rate, PQ interval, QRS duration, QT interval, and QTcF interval by study visit and treatment group within treatment period.

Frequencies and percentage of patients of investigator interpretation of ECG results (normal, abnormal clinically significant, and abnormal not clinically significant) will be summarized for patients in Safety Set by each treatment group within treatment period and study visit.

Additionally, frequencies and percentage of patients with observed QTcF >450 , >480 , and >500 msec, as well as change from baseline in QTcF >30 , >50 , and >60 msec, will be summarized for patients in the Safety Set by each treatment group within treatment period and study visit.

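### The safety baseline resets in each period, so changes that persist from Period 1 are under-recorded in Period 2 for patients who started on dasiglucagon

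*Protocol*

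**What the plan says.** Protocol Section 12.4.4 gives the rule for safety variables: "Baseline is defined as the last non-missing assessment before first dose in each treatment period". Section 13.4.4 of the German version repeats it. The next sentence sets the table layout: "All safety analyses will be summarized by treatment received within treatment period and by trial visit, if applicable". The opening of SAP Section 9 keeps that layout and adds a second one: "All safety analyses will be summarized by treatment received within treatment period and also by active treatment". The second layout combines dasiglucagon data from Periods 1 and 2.

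On treatment, Protocol Section 9.5 says "patients will be randomly assigned in a 1:1 ratio to receive either SOC only or SOC plus dasiglucagon for 4 weeks" in Period 1, and Section 9.2 says "In Treatment Period 2, all patients will receive SOC plus dasiglucagon for 4 weeks". Section 10.1 gives the resulting exposure: "The dasiglucagon treatment duration for each patient is 4 or 8 weeks".

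The SAP derives change as "value at current time point – value at baseline" (Section 6.1.7). It applies this to laboratory values, vital signs and ECG measures (Sections 9.2 to 9.4), adds shift tables for laboratory values and vital signs, and counts patients with "change from baseline in QTcF >30 , >50 , and >60 msec". All of these outputs depend on which value is taken as baseline.

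**The concern.** The rule gives the two randomized sequences different kinds of baseline in Period 2. A patient who began on SOC has a value from before any dasiglucagon. A patient who began on dasiglucagon has a value from Week 5 (or, if that is missing, from an earlier Period 1 visit), with the infusion already running. A change that developed in the first 4 weeks and persists is then part of the second patient's baseline and is subtracted out. In a shift table, a laboratory value that went from normal to high in Period 1 and stayed high appears in Period 2 as no shift.

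Summaries by treatment received put both kinds of patient in one Period 2 group, because everyone receives the same treatment. The summary pooled over both periods also mixes baselines within a patient: for a dasiglucagon-first patient, the Week 2 change is measured from a pre-drug value and the Week 9 change from an on-drug one.

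What is lost is the cumulative change over 8 weeks in the only arm exposed that long. Protocol Section 5.3.6 states that there are no data on the risks of chronic dosing, so this is a quantity a safety reader would want.

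The rule is also awkward to apply. A patient whose infusion continues has no natural first dose in Period 2, and an SOC-only patient has no dose at all in Period 1.

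**Working it through.** The plan states no figure on this point, so there is none to reproduce. The check sets the baseline rule against the visit schedule and then follows the algebra.

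**Which value becomes the Period 2 baseline.** From the Schedule of Events and SAP Sections 9.2 to 9.4:

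| Assessment | Visits after Period 1 dosing starts and up to Week 5 | Period 2 baseline, dasiglucagon-first | Period 2 baseline, SOC-first |
|---|---|---|---|
| Laboratory tests | Weeks 2, 5 | on drug | pre-drug |
| ECG | Weeks 2, 5 | on drug | pre-drug |
| Vital signs | Weeks 2, 4, 5 | on drug | pre-drug |
| Echocardiography | none | Screening | Screening |

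**Size of the attenuation.** Let
- d = the change from the pre-drug value, taken as equal in both sequences and persisting through Period 2;
- f = the fraction of d present at Week 5 (not in the documents; assumed 0 to 1);
- w = the share of Period 2 patients already on drug (0.5 from 1:1 allocation, assuming no dropout).

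Recorded Period 2 change:
- continuing patients: d − fd = (1 − f)d
- SOC-first patients: d
- combined: [w(1 − f) + (1 − w)]d = (1 − wf)d = (1 − 0.5f)d

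| f | Continuing | SOC-first | Combined |
|---|---|---|---|
| 0 | 1.0d | 1.0d | 1.0d |
| 0.5 | 0.5d | 1.0d | 0.75d |
| 1 | 0 | 1.0d | 0.5d |

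With a baseline fixed before the first-ever dose, every cell is 1.0d.

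**Illustration for the QTcF categories (all values assumed).** Take normally distributed changes, a mean shift of 10 msec, an SD of change of 15 msec, and f = 1. Then P(change > 30) = 1 − Φ((30 − mean)/SD).
- Pre-drug baseline: 1 − Φ(20/15) = 9.1%
- On-drug baseline: 1 − Φ(30/15) = 2.3%
- Combined 1:1: (9.1 + 2.3)/2 = 5.7%

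Across shifts of 5 to 20 msec and SDs of 10 to 20 msec, the pre-drug figure runs from 0.6% to 30.9% and the on-drug figure from 0.1% to 6.7%. These numbers show how the count responds to the choice of baseline. They are not a prediction for this drug.

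**The case against.** The strongest objection is that the governing text may lie elsewhere. Protocol Section 12.4 calls itself a summary and leaves detail to the SAP. SAP Section 6.1.1 (Baseline) and part of Section 10 (Changes from Planned Analysis) were not in the copy available to us. The SAP text that can be read does not restate the per-period rule. Its visit-window table (Table 3) has a single Baseline row and lists Week 5 as an ordinary visit. That table governs unscheduled and repeat values, so it does not settle the matter, but Section 6.1.1 could. This stands, and it makes the point conditional. A reader might infer that protocol and SAP disagree; nothing available shows that.

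A reader might also infer that late effects would be missed. The reverse is true: a change first arising in Period 2 is measured in full from a Week 5 baseline. Only changes already present at Week 5 are subtracted.

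Nor are such changes hidden. Period 1 tables compare on-drug values with a pre-drug baseline, next to a concurrent randomized SOC arm. Observed values are summarized by visit, and absolute QTcF above 450, 480 and 500 msec is counted without reference to baseline. It would therefore be wrong to say that QTcF increases in the dasiglucagon-first patients cannot be counted; only the Period 2 change categories miss them.

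Finally, a period-specific baseline is a workable choice. It serves SOC-first patients correctly and shows incremental change in the others. Protocol Section 5.3.6 describes the heart-rate increases seen so far as transient; if such effects have faded by Week 5, f is near 0 and little is lost. These arguments limit the consequence. They do not supply the 8-week cumulative change.

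**Conclusion.** The point holds as a minor one, on the protocol rule as written. In Period 2, persisting changes are recorded as (1 − f)d in patients who started on dasiglucagon and as 0.5d to 1.0d with the sequences combined. Halving is the limiting case f = 1, not an expected value, and f = 0 gives no loss. The result assumes equal effects in the two sequences, persistence through Period 2, 1:1 numbers without dropout, and that SAP Section 6.1.1 does not replace the rule. If Period 2 is tabulated by sequence, the combined figure does not arise, but the loss in the continuing arm remains.

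The affected outputs are changes from baseline, shift tables and QTcF-change categories in Period 2, and the same quantities in the pooled dasiglucagon summary. Adverse event incidence does not use this baseline. Echocardiography is summarized by interpretation only and has no on-drug Period 1 assessment. Safety is descriptive, so no test or error rate is touched.

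**What to change.** First check what SAP Section 6.1.1 says. Unless it already does so:

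- For Period 2 and pooled on-drug change summaries, shift tables and QTcF-change counts, take as baseline the latest available value preceding the patient's first-ever dasiglucagon dose.
- For the SOC-only column in Period 1, keep the randomization baseline.
- Show Period 2 by randomized sequence, so that 4-week and 8-week exposure can be read separately.
- Use the same wording in the protocol, its German version and the SAP.

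The period-specific baseline can stay as a supplementary display of incremental change. The cost is a short definition and a few extra table columns; every value needed is already scheduled for collection.
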